5.4.2 Sample Size Considerations

We are collecting socioeconomic data, education level, insurance type, pain and activity data at the outset with the thought that these may be related to patient experience or confound the impact of the shared decision-making tool.

PROMIS is standardized, validated tools with defined scoring methods. The three study specific tools (1. SDM Survey; 2. Post-Survey (immediately provided); 3. Post-Survey (One Month Follow-up Survey) would be scored independently using a 5 point scale for each line item. The score of 5 would apply to the most positive score and the score of 1 would apply to the least positive score.

Instrument	Scoring	Comment
Survey (Pre-appointment) (Baseline)	Yes / no or in buckets	Set initial understanding of patient sentiment prior to starting the study
PROMIS	Defined	Knee pain and activity scale
1. SDM Tool	1 to 5 point scale	Primary study outcome
2. Post-appointment Survey Follow-up	1 to 5 point scale	Same as Pre-survey and used to gauge changes in patient sentiment post-study
3. One Month Post-appointment Survey	1 to 5 point scale	Secondary study outcome

Table 2. Items 1 through 3 are the study outcome surveys.

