The variables used to measure the primary outcome will include patient willingness to proceed with specific treatment modalities as measured by the pre- and post-visit surveys.

Secondary and Exploratory Outcome Variables (if applicable)

The variables used to measure the secondary outcomes will include patient understanding of disease progression, patient understanding of the impact of treatment modalities on disease progression, patient-reported pain and functional status, and patient engagement in treatment modalities as measured by the pre- and post-visit surveys.

Study Population

The target population for this study will be persons aged 45-65, who have mild to moderate knee pain, and are seeking care from an orthopaedic surgeon specializing in total knee arthroplasty.

Number of Participants

We are seeking 200 participants. The attrition rate is assumed to be 10-20%. It may be lower due to the short follow-up period of one month, or higher given the targeted patient demographic. We anticipate enrolling 200-250 patients to account for loss to follow-up.

Study Schedule

We anticipate at least an initial patient visit that would take 30-50 minutes including an explanation of the study and obtaining consent, pre-study survey, PROMIS survey, clinical exam, Shared Decision-Making Tool discussion, and any additional questions the patient may have.

Protocol Revision History

Include the IRB approved protocol version number and date for each revision of the protocol. All version history should remain in the table and never be deleted. The oldest IRB approved version of the protocol should be listed on the top row. The most recent IRB approved version should be listed on the bottom row.

Version Date	Summary of Substantial Changes

Statement of Compliance

This document is a protocol for a human research study. The purpose of this protocol is to ensure that this study is to be conducted according to the Common Rule at 45CFR46 (human subjects) and other applicable government regulations and Institutional research policies and procedures.

Abbreviations

Abbreviation	Explanation
OA	Osteoarthritis
PI	Principal Investigator
SDMT	Shared Decision-Making Tool
UPIRSO	Unanticipated Problems Involving Risks to Subjects or Others

Glossary of Terms

Glossary	Explanation
----------	-------------

Table of Contents

Preface	2
Synopsis	3
Purpose	3
Primary Objective	3
Secondary Objective	3
Study Design	3
Study Date Range and Duration	4
Number of Study Sites	4

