4.1.1 General Design Description

This is a randomized control trial in which participants will be assigned to one of two arms. Patients in the control arm of the study will watch a short video and then receive standard of care counseling with an orthopaedic surgeon. Patients in the treatment arm of the study will watch a short video and then receive standard of care counseling with an orthopaedic surgeon that includes discussion of the SDMT. All patients will complete pre- and post-visit surveys designed to measure the severity of their knee osteoarthritis and their willingness to proceed with different treatment modalities.

All patients who are receiving care for knee osteoarthritis with one of the participating orthopaedic surgeons, and are greater than age 18 and speak English, will be eligible for inclusion in the study. The study will be conducted at Yale-affiliated clinics.

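### Table 2 scores the baseline and post-appointment surveys in different formats but calls them the same, so the pre-to-post change in willingness is undefined as written

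*Combined protocol and SAP*

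**What the plan says.** Section 5.4.2, Table 2, gives the baseline (pre-appointment) survey the scoring entry "Yes / no or in buckets" and the purpose "Set initial understanding of patient sentiment prior to starting the study". Two rows further down, the post-appointment survey is scored 1 to 5 and described as "Same as Pre-survey and used to gauge changes in patient sentiment post-study".

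The prose above the table names three study-specific tools (the SDM survey, the immediate post-survey and the one-month post-survey) that "would be scored independently using a 5 point scale for each line item". The pre-survey is not among them. The table caption likewise counts only items 1 to 3 as outcome surveys.

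Elsewhere the pre-survey is treated as an outcome instrument. Section 4.1.1 has all patients complete "pre- and post-visit surveys designed to measure the severity of their knee osteoarthritis and their willingness to proceed with different treatment modalities". The Synopsis defines the primary outcome as "patient willingness to proceed with specific treatment modalities as measured by the pre- and post-visit surveys", section 4.2.1 says the same in almost the same terms, and section 4.2.2 measures the secondary outcomes, including understanding of disease progression, by both surveys.

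Section 5.4.3 plans univariate and multivariate regression of willingness on use of the tool. It names no covariates, no change score and no recoding rule.

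**The concern.** A change score needs the same item on the same scale at both times. If the baseline answer is yes/no or a bucket and the follow-up answer is a number from 1 to 5, someone must decide what number each baseline answer stands for. The plan does not make that decision. If it is left until the data are seen, the size and even the direction of the reported change become an analyst's choice.

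There is also a possible cost in precision. If baseline willingness enters the regression as a covariate, a coarse baseline explains less of the follow-up variation than a five-level one. This matters before enrolment starts, because a finer baseline cannot be collected once the patient has been counselled.

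**Working it through.** The plan gives no figure for the pre-to-post change, so there is none to reproduce. The power statement in section 5.4.1 concerns a between-group difference in a score and does not depend on this point.

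**1. The text set side by side**

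| Place | Baseline survey | Post-appointment survey |
|---|---|---|
| Table 2, scoring | yes/no or buckets | 1 to 5 |
| Table 2, comment | sets initial sentiment | same as the pre-survey; gauges change |
| 5.4.2 prose, tools on a 5-point scale | not listed | listed |
| Table 2 caption, outcome surveys | not included | included |
| Synopsis, 4.1.1, 4.2.1, willingness | measured | measured |
| Rule converting one format to the other | none | none |

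The prose and the caption agree with the baseline row that the pre-survey stands apart from the 1-to-5 tools, so a slip in a single cell is not the most natural reading.

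**2. Effect of the mapping on a within-arm change**

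Assumed inputs (not in the documents): share answering yes at baseline p = 0.7; post-visit mean 3.5.

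Baseline mean = p × (code for yes) + (1 − p) × (code for no); change = post-visit mean − baseline mean.

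- No/yes coded 1/5: 0.7 × 5 + 0.3 × 1 = 3.8; change = 3.5 − 3.8 = −0.3.
- No/yes coded 2/4: 0.7 × 4 + 0.3 × 2 = 3.4; change = 3.5 − 3.4 = +0.1.

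Both codings are defensible and they give opposite signs.

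**3. Effect on the between-arm comparison**

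The mapping shifts the between-arm difference in change by (code for yes − code for no) × (difference between arms in p). With equal baseline shares this is zero. With a chance imbalance it is 4 times the difference in shares under 1/5 coding and 2 times under 2/4 coding. The comparison of post-visit scores alone does not involve the mapping.

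**4. Precision, only if baseline willingness is a covariate**

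Assumptions: bivariate-normal latent willingness with pre/post correlation ρ of 0.3, 0.5 or 0.7; baseline entered as categories; comparator a baseline with five equal levels. Residual share = 1 − Var(E[Y | baseline category]) / Var(Y).

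Single item, follow-up in five equal levels scored 1 to 5 (ratios taken before the shares were rounded):

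| Baseline format | Residual share at ρ = 0.3 / 0.5 / 0.7 | Ratio to five-level |
|---|---|---|
| Five equal levels | 0.928 / 0.794 / 0.582 | 1 |
| Yes/no, 50/50 | 0.948 / 0.850 / 0.687 | 1.022 / 1.071 / 1.181 |
| Yes/no, 70/30 | 0.953 / 0.867 / 0.728 | 1.028 / 1.092 / 1.251 |
| Three equal buckets | 0.936 / 0.815 / 0.620 | 1.009 / 1.027 / 1.066 |

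With a continuous follow-up, the 50/50 ratios are 1.025 / 1.084 / 1.228.

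If items are summed (an assumption; simulation of 1,000,000 patients, inter-item correlation 0.5), the 50/50 ratios depend on what persists between visits:

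| Summed items | Only the shared trait persists | Item-specific parts persist at the same correlation |
|---|---|---|
| 4 items | 1.008 / 1.025 / 1.058 | 1.014 / 1.043 / 1.111 |
| 6 items | 1.008 / 1.024 / 1.057 | 1.011 / 1.034 / 1.090 |

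**The case against.** The strongest reply is that the table may be loosely worded and the instrument sound. The column is headed scoring, not response options. The post-survey could repeat the same questions in a different format. The buckets could already be five ordered levels. The baseline row could be summarising a mixed form, since the plan also states "We are collecting socioeconomic data, education level, insurance type, pain and activity data at the outset". The survey forms are not in the text, so none of this can be ruled out. If the form does use five levels, the defect is one table entry.

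A second reply is that the change statement in Table 2 concerns sentiment, that no section calls the primary endpoint a change score, and that Table 2 puts the label "Primary study outcome" on the SDM Tool row and not on the survey used to gauge change. The within-arm change does not estimate the effect of the tool in any case.

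A third is that the precision figures rest on a covariate the plan does not name and on an assumed model, and run from nil to 25%.

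All three stand as limits on the reach of the point. They do not remove it. The text gives no mapping, assigns the survey the job of gauging change, and requires the pre-survey for the primary outcome. Its scoring must therefore be defined whichever model is used. The precision figures are secondary, and the conclusion does not need them.

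**Conclusion.** The concern holds. As written, the two scoring entries cannot both describe the same survey, and a like-for-like pre-to-post change in willingness, or in understanding, is undefined. This should be fixed, but it does not invalidate the trial: the randomised comparison of post-visit 1-to-5 scores remains available and the stated power is untouched.

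Confidence is high for the conflict in the text. The sign reversal is an illustration on assumed figures. Confidence in the precision loss is low to moderate: for a 50/50 yes/no baseline it is about 2% to 18% for a single item with a five-level follow-up and about 1% to 6% for a sum of 4 to 6 items, or up to 11% if item-specific parts also persist. It is nil if the buckets are already five ordered levels, and it arises only if baseline willingness is a covariate, which section 5.4.3 neither specifies nor excludes.

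**What to change.** 1. In the pre-survey and in Table 2, give the willingness and understanding items the same 1-to-5 response options as in the post-surveys. Leave demographic items as yes/no or buckets. If the form already has five ordered levels for these items, correct only the Table 2 scoring entry. If the form cannot be changed, state the mapping in section 5.4.2 before any data are seen; this removes the contradiction but does not recover a finer baseline.
2. In section 5.4.3, prespecify the post-visit willingness score regressed on arm and on the baseline score of the same items, with the univariate result reported alongside. This goes beyond curing the scoring conflict, but it settles how the baseline is used.
3. Reconcile the primary-outcome label on the SDM Tool row of Table 2 with the Synopsis and section 4.2.1.

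The cost is new response options for some items on one existing survey, one sentence in section 5.4.3 and one label in Table 2. No visit or patient is added.

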5.4.3 Planned Analyses

We plan to perform univariate and multivariate regression analyses to assess associations between the SDMT and the patient willingness to proceed with specific treatment modalities. Additional univariate and multivariate regression analyses will be performed to assess our secondary study outcomes.

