4.2 Outcome Variables

4.2.1 Primary Outcome Variables

The variables used to measure the primary outcome will include patient willingness to proceed with specific treatment modalities as measured by the pre- and post-surveys.

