5.4 Statistical Method

5.4.1 Statistical Design

Power Analysis

Statistical Power is determined by the estimated mean and standard deviation of one primary endpoint or composite endpoint to determine ending sample size in each group (test and control). The study power varies with Standard Deviation and Expected Difference in Performance between control and investigational groups. The power is the probability the study will detect a statistical difference between the two groups based on the expected standard deviation and mean difference between the two groups.

This study for which a power of 0.8 is sufficient and we expect a difference in score between the test group and control group to be at least 20% and a standard deviation of 10 points or less. Even if the difference between groups drops to 10% with a standard deviation of 10 points our target sample size of 200 patients is sufficiently powered.

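### The regression plan does not say that the primary model conditions on each patient's own pre-visit willingness, which the trial already collects; specifying it would gain precision at almost no cost.

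*Combined protocol and SAP*

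**What the plan says.** - **Analysis.** Section 5.4.3 plans "univariate and multivariate regression analyses to assess associations between the SDMT and the patient willingness to proceed", and says the same kind of analyses will serve the secondary outcomes. It names no covariate, response form or primary model.
- **Baseline data.** Section 5.4.2 says the trial collects "socioeconomic data, education level, insurance type, pain and activity data at the outset", because these may relate to patient experience or confound the effect of the tool. Pre-visit willingness is not among them.
- **Willingness is measured before the visit.** Section 4.1.1 says: "All patients will complete pre- and post-visit surveys designed to measure the severity of their knee osteoarthritis and their willingness to proceed". Section 4.2.1 defines the primary outcome as "patient willingness to proceed with specific treatment modalities as measured by the pre- and post-surveys".
- **Scoring.** In the instrument table of 5.4.2 the baseline survey is scored "Yes / no or in buckets". The post-appointment survey is scored 1 to 5 and described as "Same as Pre-survey and used to gauge changes in patient sentiment post-study". The same table labels a different row, the SDM Tool, as the primary study outcome.
- **Power.** Section 5.4.1 says "a power of 0.8 is sufficient" and holds 200 patients adequate even for a 10% difference with an SD of 10 points.

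**The concern.** In a randomised trial, confounding is handled in expectation by the allocation. What a baseline covariate adds is removal of outcome variance and correction of chance imbalance, and the baseline value of the outcome is usually the best candidate. Here it is already collected, but nothing in the plan commits the analysis to using it.

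Three analyses fit the wording: post-visit response alone, change from baseline, or post-visit response adjusted for baseline. They differ in precision, and the plan does not choose. At stake are a wider standard error than necessary and an estimate that moves with any chance difference between arms in prior willingness. The choice would also be left until the data are in hand. The same holds for secondary outcomes asked both before and after the visit, such as understanding of progression.

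**Working it through.** **Inputs.** From the documents: N = 200, target power 0.8, fallback difference 10% with SD 10 points (5.4.1); baseline scored yes/no or in categories, post-survey 1 to 5 (5.4.2). Assumed, because not stated: 1:1 allocation (100 per arm), two-sided 5%, and r = 0.3 to 0.7. A linear model is used because 5.4.1 speaks of means and SDs.

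**1. The plan's own figure.** Patients per arm = 2(1.96 + 0.842)² × SD²/difference².

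| Reading of 10% | Needed per arm | Power at 100 per arm |
|---|---|---|
| 10 points, SD 10 | 16 | about 1.00 |
| 5 points (mean 50), SD 10 | 63 | 0.94 |
| 4 points (mean 40), SD 10 | 99 | 0.81 |

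The scale and reference mean are not given, so 200 has no unique derivation. The effect that 100 per arm detects with 80% power is (1.96 + 0.842) × √(2/100) = 0.396 SD.

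**2. Relative variance of the arm effect, baseline and outcome on one scale with equal variances.** Post-only is 1, change score 2(1 − r), adjusted 1 − r².

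| r | Change | Adjusted | Power at 0.4 SD: post-only / change / adjusted |
|---|---|---|---|
| 0.3 | 1.40 | 0.91 | 0.807 / 0.667 / 0.843 |
| 0.5 | 1.00 | 0.75 | 0.807 / 0.807 / 0.904 |
| 0.7 | 0.60 | 0.51 | 0.807 / 0.955 / 0.977 |

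Since 2(1 − r) − (1 − r²) = (1 − r)², adjustment beats the change score at every r below 1. This table is the best case; it ignores the coarse baseline scoring.

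**3. With the baseline as scored (yes/no).** Splitting a normal baseline at its median multiplies r by √(2/π) = 0.798. The variance factor is then 1 − (0.798r)². Take an effect with 85% unadjusted power, (1.96 + 1.036) × √(2/100) = 0.424 SD. Adjusted power is Φ(2.996/√factor − 1.96).

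| Latent r | Variance factor | Equivalent N = 200/factor | Power (unadjusted 85%) |
|---|---|---|---|
| 0.3 | 0.943 | 212 | 87% |
| 0.5 | 0.841 | 238 | 91% (0.905) |
| 0.7 | 0.688 | 291 | 95% |

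Simulating a 1-to-5 outcome with a yes/no baseline gave the same picture: about 87%, 91% and 95%.

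**4. Chance imbalance.** With 100 per arm the baseline difference has standard error √(2/100) = 0.141 SD, so 95% of trials fall within ±0.277 SD. The chance of exceeding 0.2 SD is 2(1 − Φ(0.2/0.141)) = 0.157. An imbalance of 0.277 SD shifts an unadjusted post-visit contrast by r × 0.277 = 0.08, 0.14 or 0.19 SD at r = 0.3, 0.5 or 0.7.

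**5. Is a change score available?** Subtracting a yes/no or categorised answer from a 1-to-5 answer is not a defined quantity. A covariate need not share the outcome's scale, so adjustment works with the survey as it stands.

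**The case against.** The strongest reply is that the plan is silent, not wrong, and all of the following stands.

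- **The plan does not exclude baseline.** A reader might infer that 5.4.3 rejects adjustment. It does not: the multivariate model could include pre-visit willingness. The list in 5.4.2 describes what is collected and why; it is not presented as the model's covariate list. The primary outcome wording and the stated aim of gauging change suggest that baseline was meant to enter somehow.
- **Lost power is not shown on the plan's own figures.** A reader might infer that the trial is underpowered without adjustment. On the literal reading, 10 points with SD 10, power is about 1.00 either way. Section 5.4.1 calls 0.8 sufficient; it does not say that the unadjusted model has 80%. Effects near 0.4 SD are an assumption here.
- **The textbook gain is too large for this baseline.** Using 1 − r² directly would equate 200 patients with 267 at r = 0.5 (200/0.75) or 392 at r = 0.7 (200/0.51). With yes/no scoring these become about 238 and 291.
- **Imbalance is not bias.** Randomisation leaves the unadjusted contrast unbiased on average, and its standard error already reflects chance imbalance. At r = 0.5 an imbalance of 0.2 SD moves the estimate by 0.1 SD, less than the 0.141 SD standard error.
- **The primary instrument is unclear.** Only the post-appointment survey is said to match the pre-survey, while the table gives the primary label to the SDM Tool. The matching baseline item must be identified before adjustment can be carried out.

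None of this removes the point. Silence leaves a less precise analysis open, and the univariate model certainly uses no baseline information.

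**Conclusion.** The point holds as a low-cost improvement that should be made, not as an error that invalidates the trial. The documents show that pre-visit willingness is collected, that no section commits the model to conditioning on it, and that it is missing from the listed baseline variables.

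The direction of the gain is secure: adjustment is at least as precise as either alternative, apart from the few degrees of freedom spent. Its size is uncertain because r is not given. With a yes/no baseline it is roughly 2 to 10 percentage points of power from a starting point of 85%, and 1 − r² bounds the gain from above. If the effect is as large as 10 points with SD 10, the benefit is a narrower confidence interval only. The documents do not support the stronger claims that baseline is excluded, that the trial lacks power, or that the unadjusted estimate is biased on average.

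**What to change.** - **In 5.4.3,** state that the primary analysis regresses each post-visit willingness outcome on randomised arm, with the corresponding pre-visit willingness item as a covariate (categorical where the item is yes/no or bucketed). Keep the unadjusted model as supportive. Treat secondary outcomes that have a pre-visit measure the same way.
- **In 5.4.2,** add pre-visit willingness to the baseline variables. State that the primary willingness outcome comes from the post-appointment survey that matches the pre-survey, and reconcile this with the table row that labels the SDM Tool the primary outcome.

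The cost is a few sentences of wording and one or a few model degrees of freedom. No new data, patients or procedures are needed. The wording should be settled before outcome data are examined, so that the choice of model cannot depend on the results.

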5.4.4 Analysis of Subject Characteristics (if applicable)

Not applicable

5.4.5 Interim Analysis (if applicable)

Not Applicable

5.4.6 Handling of Missing Data

Patients who have missing data will be excluded from the analysis.

6 Trial Administration

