5.1 Study Procedures

Potential subjects will be identified by the PI and participating orthopaedic surgeons. The PI and Sub-I will recruit potential subjects for this study.

Subjects will be consented in a private room by a designated member of the study team. Each subject will be consented in the language appropriate and presented with a consent form, written in that language. All aspects of the study will be discussed with the potential subject including the reason the subject is being asked to participate, the schedule of visits, the study activities that will occur, and the risks and benefits of participation. The subject will then have an opportunity to ask any questions they have. Once all questions have been answered and the subject feels that he/she would like to participate, the designated member of the research team will obtain verbal consent for the study.

A subject's capacity to provide consent will be evaluated by a member of the consenting staff based on the questions the subject asks about his/her involvement in the study as well as by asking the subject questions pertaining to aspects of the study.

Eligible patients who agree to participate and provide verbal informed consent, will be randomized to participate in either the Control Group or Intervention Group. Both groups will complete the PROMIS Computer Adaptive Test and pre-survey as well as watch a short video providing general information about knee OA. The intervention for the intervention group will be the surgeon utilizing the SDMT during the visit. Both the control and intervention group will complete the post-event survey immediately after completing the control or intervention and then 1 month later.

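### The missing-data rule in 5.4.6 excludes whole patients without saying for which outcome, so it either discards observed immediate outcomes or leaves the one-month comparison to completers only

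*Combined protocol and SAP*

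**What the plan says.** The whole missing-data plan is the sentence in 5.4.6: "Patients who have missing data will be excluded from the analysis". The unit removed is the patient. The sentence does not say which variable, survey or time point must be missing, or whether removal applies to the study as a whole or to each analysis. No other section limits it.

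The surrounding plan is as follows.

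- **Time points.** Under 5.1, both groups "will complete the post-event survey immediately after completing the control or intervention and then 1 month later".
- **Roles.** Table 2 in 5.4.2 marks the SDM Tool row "Primary study outcome" and the one-month survey as secondary. Each line item is scored 1 to 5.
- **Attrition.** Synopsis, Number of Participants: "The attrition rate is assumed to be 10-20" percent. The next sentence says "It may be lower due to the short follow-up period of one month", and adds that it may be higher because of the patients targeted. The provision made is: "We anticipate enrolling 200-250 patients to account for loss to follow-up".
- **Analysis.** Section 5.4.3: "We plan to perform univariate and multivariate regression analyses to assess associations between the SDMT and the patient willingness" to proceed with specific modalities, and then: "Additional univariate and multivariate regression analyses will be performed to assess our secondary study outcomes". It names no analysis set, imputation or sensitivity analysis.

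**The concern.** A patient-level exclusion with no stated scope allows two analyses of the same trial, and the text does not choose between them.

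- **Literal reading.** One missing survey removes the patient from everything. Immediate outcomes that were observed in randomised patients are thrown away because of something that happened, or did not happen, a month later.
- **Analysis-by-analysis reading.** The immediate outcome is kept. The one-month outcome is analysed in completers only, and the immediate score, the best available predictor on file, is not used to inform a missing one-month score. The univariate and multivariate regressions may also run on different patients, because 5.4.2 collects education, insurance and socioeconomic data that can be incomplete.

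In both cases the set analysed is chosen by events after randomisation. That biases the arm comparison if loss is related to outcome differently in the two arms. This is plausible here, though the documents do not assert it: engagement with treatment is itself a secondary outcome (4.2.2), and patients who disengage may be the ones who do not return the one-month survey. Covariate gaps unrelated to arm would mainly cost precision.

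**Working it through.** **1. The plan's own enrolment figure.** Inflating a target of 200 for loss d gives N = 200/(1 − d).

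- d = 0.20: 200/0.80 = 250, the top of the stated range.
- d = 0.10: 200/0.90 = 222.2, so 223, inside the range.
- The bottom of the range, 200, allows for no loss.

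The allowance reproduces. It restores the count of completers but does not affect who they are.

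**2. Patients affected at 10-20% loss.**

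| Enrolled | Lost | One-month outcome observed |
|---|---|---|
| 200 | 200 × 0.10 = 20 to 200 × 0.20 = 40 | 180 to 160 |
| 250 | 250 × 0.10 = 25 to 250 × 0.20 = 50 | 225 to 200 |

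On the literal reading the last column is also the immediate analysis set. On the other reading the immediate set stays at 200 or 250, apart from other gaps. The Synopsis gives 10-20% as overall attrition and ties it to one month by context only. Missing covariates or single items could add to the literal losses; the documents give no figure for these.

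**3. Bias, as an illustration.** Let m be the fraction lost in an arm and δ the completer mean minus the non-completer mean. The full-arm mean is the completer mean minus mδ, so the completers-only difference is shifted by

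bias = m_I δ_I − m_C δ_C (I = intervention, C = control).

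Assumed, with no source in the documents: equal loss in both arms, and non-completers 0.25-0.75 points less willing than completers in one arm only.

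- 10% loss: 0.10 × 0.25 = 0.025 to 0.10 × 0.75 = 0.075 points.
- 20% loss: 0.20 × 0.25 = 0.05 to 0.20 × 0.75 = 0.15 points.

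The shift favours the SDMT if the gap is in the intervention arm, goes against it if in the control arm, and is zero if loss and gap are the same in both.

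**4. False-positive rate with no true effect.** Two-sample t test, two-sided 0.05, 1:1 allocation, SD 1.0 (all assumed). SE = SD × √(2/n); noncentrality = bias/SE.

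| Enrolled, loss | n per arm | SE | Noncentrality | False-positive rate |
|---|---|---|---|---|
| 200, 10% | 90 | 0.149 | 0.17 to 0.50 | 5.3% to 7.9% |
| 200, 20% | 80 | 0.158 | 0.32 to 0.95 | 6.1% to 15.6% |
| 250, 10% | 112.5 | 0.133 | 0.19 to 0.56 | 5.4% to 8.7% |
| 250, 20% | 100 | 0.141 | 0.35 to 1.06 | 6.4% to 18.4% |

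With the bias held fixed, the larger trial has the higher false-positive rate, because the standard error shrinks and the bias does not.

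**5. Power depends on the scale.** Section 5.4.1 gives the difference in percent and the SD in points.

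- If 10% means 10 points with SD 10, power is above 0.999 at 80 per arm.
- If 10% means a tenth of the 4-point range of a 1-5 item (0.4) with SD 1.0, power is 0.80 at 100 per arm, 0.76 at 90 and 0.71 at 80.

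Both conversions are assumptions, so the effect of attrition on power cannot be settled from the text.

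**The case against.** **The bias is conjecture.** The gap, the SD and its confinement to one arm are all assumed, and the scenario has the tool altering who drops out while leaving the outcome unchanged. Milder assumptions give little: with a 0.5-point gap in both arms and 10% against 20% loss, the bias is 0.5 × (0.20 − 0.10) = 0.05 points, and at SD 1.0 the false-positive rate is about 6%. This stands. The figures show scale and are not a forecast.

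**The ordinary reading is analysis by analysis.** Section 5.4.3 plans the secondary-outcome regressions separately, and on that reading one-month loss touches only an outcome that Table 2 calls secondary. This is fair, and it limits the consequence. It does not settle the text, which removes patients and names no analysis.

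**Imputation is not a cure.** If loss depends on the unseen one-month score, imputing from the immediate score leaves bias. This is correct, and is why a delta analysis belongs with it. Multiple imputation is also only one acceptable method.

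A reader might go further than the documents allow in three ways.

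- *That the immediate result will be biased.* This needs both the literal reading and loss related to outcome differently by arm; neither is established.
- *That power is safe, or that it is lost.* Section 5.4.1 mixes percent and points, so it supports neither.
- *That the SDM survey is an arm comparison spoiled by this rule.* Section 5.1 does not list it among what both groups complete, and 5.4.2 does not say that controls receive it.

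**Conclusion.** The point holds as a gap in the plan that should be fixed. That 5.4.6 is unrestricted is certain from the text. Followed literally, it discards the observed immediate outcomes of 20-40 of 200 patients, or 25-50 of 250, at the protocol's assumed attrition, which the protocol says may be higher. Followed analysis by analysis, it leaves the one-month outcome to completers and lets the multivariate models lose patients with a missing covariate. Enrolling up to 250 answers the count and not the selection.

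How much bias results is unknown. The illustration (0.025-0.15 points, and about 5-16% false positives with 200 enrolled) rests wholly on the assumed one-arm gap of 0.25-0.75 points and SD 1.0. The bias is zero if loss and gap are equal in both arms. Confidence is medium for that reason. No conclusion is drawn about power.

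**What to change.** Replace 5.4.6 with wording such as:

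> Each outcome is analysed by assigned arm in all randomised patients with that outcome observed, whatever their status on other surveys. A survey with some items missing is scored from the answered items under a rule fixed before data are seen. Missing baseline covariates and missing one-month scores are multiply imputed, with arm, baseline response and immediate post-visit score in the model, so the one-month analysis also includes patients who did not return that survey. Loss is reported by arm for each survey. A sensitivity analysis shifts the imputed one-month scores by prespecified deltas in each arm separately.

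The team should fix the item rule and the deltas before seeing data. Apply this to the SDM survey as an arm comparison only if both arms complete it, and state in 5.1 whether they do.

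The cost is a protocol modification reported to the IRB (6.2) and a little more analysis. No patients or visits are added. What remains is loss that depends on the unseen one-month score: imputation does not remove that bias, and the delta analysis only shows how far the result would move.

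The 8 August 2022 close of collection (Synopsis, 4.1.2, 6.12) also bears on one-month completeness, but it depends on enrolment timing that the text does not give and should be handled as a separate issue.
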